#### **Statistical Methods:**

**Safety Analysis:** All safety data collected will be listed and be summarized, as appropriate, by treatment groups.

**Efficacy analysis:** Since the efficacy endpoints will be evaluated for exploratory purpose, formal statistical comparisons will not be made for these endpoints.

**Exploratory analysis:** Point estimates and 95% CI will be calculated for all continuous exploratory parameters (i.e. MRI-PDFF and laboratory values). For categorical variables, descriptive statistics will be calculated with count and percentage of subjects in each category by treatment group. Descriptive statistics will be provided for all pharmacokinetic parameters.

Sample Size: Due to exploratory nature of this study, no formal power calculations were used to determine sample size. The number of subjects was chosen based on clinical experience with other similar proof of concept studies.

Approved by: [name] [name] Protocol No.: SARO.17.010

Confidential Page 12 of 80

# **ABBREVIATIONS**

Abbreviation	Definition
AE	adverse event
ALP	alkaline phosphatase
ALT	alanine aminotransferase
aP2	adipocyte fatty-acid-binding protein
API	active pharmaceutical ingredient
Apo	Apo lipoprotein
APTT	activated partial thromboplastin time
AST	aspartate aminotransferase
BLM	baseline measure
BMI	body mass index
BP	blood pressure
BUN	blood urea nitrogen
CAP	Controlled Attenuation Parameter
CHL	Cadila Healthcare Limited
CPK	creatine phosphokinase
CSR	Clinical study report
CTCAE	Common Terminology Criteria for Adverse Events
eCRF	Electronic case report form
CYP	Cytochrome450
DMC	Data Monitoring Committee
ECG	Electrocardiogram
ЕСНО	Echocardiogram
EOT	End of treatment
eCRF	Electronic case report form
eGFR	Estimated glomerular filtration rate
FA	fatty acids
FFA	Free fatty acid
FSIVGTT	frequently sampled intravenous glucose tolerance test
GCP	Good Clinical Practice
GGT	gamma glutamyltransferase
HbA1c	glycosylated hemoglobin
HCV	hepatitis C virus
HDL	High-density lipoprotein
HIV	Human Immunodeficiency Virus
HBsAg	Hepatitis B surface antigen
ICF	Inform consent form
ICH	International Council for Harmonisation
IEC	Independent Ethics Committee
INR	international normalized ratio

[figure not shown]
Approved by:	Protocol No.: SARO.17.010
[name] [name]	Version No.: 7.0

Confidential Page 13 of 80

Abbreviation	Definition
IP	Investigational product
IRB	Institutional Review Board
LDL	Low-density lipoprotein
LFT	liver function test
LOCF	last observation carried forward
LPL	lipoprotein lipase
LT	liver transplantation
MCH	mean corpuscular hemoglobin
MCHC	mean corpuscular hemoglobin concentration
MCV	mean corpuscular volume
MITT	modified Intent-to-treat
MPV	mean platelet volume
MRI-PDFF	magnetic resonance imaging-proton density fat fraction
MRE	magnetic resonance elastography
NAFLD	Nonalcoholic fatty liver disease
NASH	Nonalcoholic steatohepatitis
NME	New molecular entity
OD	once daily
PP	per protocol
PPAR	peroxisome proliferator-activated receptors
PT	prothrombin time
QoL	Quality of life
RBC	red blood cell
RFT	renal function test
SAE	serious adverse event
SAP	Statistical Analysis Plan
sdLDL	small dense low-density lipoprotein
SOP	standard operating procedure
T2DM	Type 2 diabetes mellitus
TC	total cholesterol
TE	Transient Elastography
TG	Triglycerides
TT	thrombin time
TZDs	thiazolidinediones
VLDL	very low-density lipoprotein
WBC	white blood cell

Approved by: [name] [name] Protocol No.: SARO.17.010

Confidential Page 14 of 80

### 1 STUDY FLOW CHART

[figure not shown]
Protocol No.: SARO.17.010

[figure not shown]
Confidential Page 18 of 80

[figure not shown]
Approved by: [name] [name] Protocol No.: SARO.17.010

Confidential Page 19 of 80

Confidential Page 20 of 80

Protocol No.: SARO.17.010

CONFIDENTIAL
PAGE 21 OF 80

### **2 INTRODUCTION**

### 2.1 MEDICAL BACKGROUND

Nonalcoholic fatty liver disease (NAFLD) is the most common form of chronic liver disease (Angulo, 2002; Wieckowska and Feldstein, 2005) with an estimated global prevalence of 25% (Younossi et al., 2015). The severity of NAFLD ranges from simple hepatic steatosis to nonalcoholic steatohepatitis (NASH) and around 7–30% have NASH, of which 10–20% progress to liver cirrhosis, for which the only treatment is liver transplantation (LT) (Younossi et al., 2015).

Non-alcoholic steatohepatitis is now the fastest growing and second most etiology of liver disease among new waitlist registrants for LT. Simultaneously to this course, the development and or recurrence of NASH after LT is certain to impose significant challenges. The genetic predisposition, immunosuppressive regimen and metabolic syndrome risk factors all play a role in the development of NAFLD/NASH after LT. In fact, NAFLD tends to recur 90% of the time after LT (Bhati et al. 2017) and patients with post-LT are at much higher risk of metabolic conditions such as diabetes, hypertension, hyperlipidemia and obesity. These metabolic conditions pose considerable risk to LT patients with NAFLD as these conditions or linked to post-LT mortality.

Generally, control of lipids and weight loss by diet and exercise are recommended for treatment of patients with NAFLD, including NASH, but their long-term effectiveness is questionable because many patients are unable to comply with the required dietary and lifestyle changes (Bellentani et al., 2008; Musso et al., 2010). Therefore, an alternative and effective pharmacotherapeutic approach is needed. Moreover, a multidisciplinary approach is required to manage transplanted patients with NASH, which include cardiovascular medicine, endocrinology, surgery, nutrition, and behavioral psychology, etc., to reduce identified risk factors.

### 2.2 RATIONALE FOR CONDUCTING THE STUDY

Saroglitazar magnesium is a novel predominately PPAR $\alpha$  agonist and moderate PPAR $\gamma$  agonist. Pre-clinical studies with Saroglitazar magnesium using various animal models wherein, EC50 of PPAR $\alpha$ : PPAR $\gamma$  >300; favorably modulated the lipid and glucose profile. Extensive preclinical safety pharmacology, pharmacokinetics and toxicological studies of

PAGE 22 OF 80

Saroglitazar magnesium showed favorable results. It was found to have superior or equivalent safety and efficacy profile compared to marketed fibrates or thiazolidinediones (TZDs) in preclinical studies.

PPARα activation by Saroglitazar magnesium increases the hepatic oxidation of fatty acids (FA) and reduces the synthesis and secretion of TG. This, in turn, increases diversion of FA from peripheral tissues (e.g., skeletal muscle and fat tissue) to the liver, thereby decreasing both FA synthesis and delivery of TG to peripheral tissues. In addition, Saroglitazar magnesium causes increased lipolysis and elimination of TG-rich particles from plasma by activating lipoprotein lipase (LPL) and reducing production of apolipoprotein C-III (an inhibitor of LPL activity). Consistent with the above mechanism, Saroglitazar magnesium was also found to reduce plasma LDL cholesterol. PPARα activation by Saroglitazar magnesium also induces an increase in the synthesis of apolipoproteins, A-I, A-II and HDL cholesterol.

Although Saroglitazar magnesium is predominantly a PPARα agonist, it also causes activation of PPARγ and regulates the transcription of insulin-responsive genes involved in the control of glucose production, transport and utilization. Saroglitazar magnesium increases the expression of numerous PPARγ-responsive genes involved in carbohydrate and lipid metabolism, including adiponectin, adipocyte fatty-acid-binding protein (aP2), LPL, fatty acid transport protein and fatty acid translocase (CD36). By increasing the expression of these genes, Saroglitazar magnesium decreases the post-prandial rise of plasma free fatty acids (FFA), improves post-absorptive insulin-mediated suppression of hepatic glucose output, reduces the metabolic burden on liver and muscle and promotes glucose utilization. Robust antidiabetic and insulin sensitizing effects of Saroglitazar magnesium were observed in preclinical models, in which hyperglycemia and/or impaired glucose tolerance is a consequence of insulin resistance in target tissues.

Peroxisome proliferator-activated receptors (PPARs), the largest family of nuclear receptors, are now a prime focus of NAFLD/NASH research. There are three subtypes, PPAR- $\alpha$ ,  $\gamma$  and  $\delta$ . Upon receptor activation, all bind the retinoid X receptor (RXR) to form transcriptionally active heterodimers. PPAR $\alpha$  is primarily expressed in tissues that use fatty acids as a fuel, such as the liver, muscle, heart and kidneys. In contrast, PPAR $\gamma$  is found predominantly in adipose tissue where it mediates differentiation of pre-adipocytes (adipogenesis), lipid storage and insulin action.

Approved by: Protocol No.: SARO.17.010
[name] [name] Version No.: 7.0

PAGE 23 OF 80

PPARα is central to hepatic lipid homeostasis. When hepatic fatty acid levels increase, PPARα is activated, leading to transcription of such genes as liver fatty acid binding protein (LFABP), acyl-CoA oxidase (ACO), cytochrome P450 (CYP) 4A, microsomal triglyceride transfer protein (MTTP) and apolipoprotein B100 (apoB100). The net effect is catabolism and clearance of fatty acids. It has recently been appreciated that the liver may respond to newly synthesized fatty acids differently from those 'recycled' from peripheral stores, and this discrimination is mediated by selective effects on PPARa. This may explain why PPARa activation does not appear to occur as an adaptive response in fatty liver disease, when it would be an effective pathway to enhance insulin sensitivity and suppress inflammatory recruitment. Thus, while pharmacologic PPARα activation effectively 'cured' fibrosing steatohepatitis in a murine, dietary model, the efficacy of such agents is less clear in humans. PPARy is found predominantly in adipocytes. It has both opposite and complementary functions to PPARa. Thus, PPARy activation leads to differentiation of adipocytes from pre-adipocytes in-vitro. This increases the lipid storage capacity of the adipose mass, and in animals, also increases the number of small, insulin-sensitive adipocytes so as to improve insulin sensitivity. Increasingly, the importance of PPARy is being recognized in the liver, despite the relatively low levels of expression normally found there. Steatosis is often associated with increased hepatocyte expression of PPARy.

Therefore, peroxisome proliferator-activated receptor (PPAR) agonists are known to lower high blood triglyceride levels (PPAR $\alpha$  agonists) and improve insulin resistance (PPAR $\gamma$  agonists), and may offer a potential treatment not only for patients with NAFLD or NASH but also for post liver transplant NAFLD/NASH.

### 2.3 DRUG PROFILE

Several research groups have developed or are attempting to develop dual PPAR $\alpha/\gamma$  agonist, some of which may eventually reach desirable clinical efficacy and safety end point. But if the agonist has higher PPAR $\gamma$  binding properties then several of the side effects such as edema, weight gain, bone effects and cardiovascular complications may occur. Therefore, there has been an increasing interest to develop new molecular entities which can treat insulin resistance, lower plasma glucose in diabetic patients and improve lipid profile without weight gain and cardiovascular risk.

Approved by: [name] [name] Protocol No.: SARO.17.010

CONFIDENTIAL PAGE 24 OF 80

If a new Chemical Entity (NCE) having a superior PPAR-α agonist activity with a moderate
PPAR- $\gamma$ agonist activity is developed, it may have a more desirable clinical profile with no
edema or weight gain effects.

### 2.4 RISK AND BENEFIT

The safety and tolerability of Saroglitazar magnesium is well defined on the basis of preclinical and clinical studies (Phase 1 to Phase 3). This study will further evaluate the safety, tolerability and efficacy of Saroglitazar magnesium in liver transplant recipients with NAFLD.

Saroglitazar magnesium is approved in India at the doses of 2 mg and 4 mg QD for the treatment of "diabetic dyslipidemia" and "hypertriglyceridemia with type 2 diabetes mellitus (T2DM) not controlled by statin therapy". Overalll, Saroglitazar magnesium has shown to be well-tolerated during studies with no major safety concerns. Therefore we do not expect significant risk from the experimental medication. A theoretical benefit of participation is that treatment may improve NAFLD in liver transplant recipients. Though short-term treatment is of little consequence over the long term,

Approved by:	Protocol No.: SARO.17.010
[name] [name]	Version No · 7 0

CONFIDENTIAL
PAGE 25 OF 80

information about a given subject's response to this therapy could guide their clinician in making long-term therapeutic decisions. Thus, a potential benefit of the study is to determine the safety, tolerability and efficacy among subjects. As for risk, the protocol is designed to minimize the risks to participants while maximizing the potential value of the knowledge it is designed to generate. On balance, we believe there is a reasonable prospect for individual and generalized benefit when compared to the risk of participation.

Approved by: [name] [name] Protocol No.: SARO.17.010

CONFIDENTIAL
PAGE 26 OF 80

## 3 STUDY OBJECTIVES

The objective of this study is to evaluate the safety, tolerability and efficacy of Saroglitazar magnesium in liver transplant recipients with NAFLD.

### 3.1 PRIMARY OBJECTIVE

To assess the safety of Saroglitazar magnesium 4 mg in liver transplant recipients with NAFLD over 24 weeks of treatment.

### 3.2 SECONDARY OBJECTIVES

- 1 Changes in hepatic fat as determined by MRI-PDFF and MRE from baseline to end of treatment (EOT).
- 2 Changes in metabolic flexibility from baseline to EOT.
- 3 Changes in markers of insulin resistance [frequently sampled intravenous glucose tolerance test (FSIVGTT), glycosylated hemoglobin (HbA1c) and fructosamine] from baseline to EOT.
- 4 Changes in serum liver enzymes from baseline to EOT.
- 5 Changes in serum lipids from baseline to EOT.
- 6 Changes in atherogenic lipoprotein which including small dense low-density lipoprotein (sdLDL), LDL size and concentration, subtypes of very low-density lipoprotein (VLDL), high-density lipoprotein (HDL) from baseline to EOT.
- 7 Change in Quality of life score from baseline to EOT.
- 8 Pharmacokinetics of Saroglitazar following first dose and last dose.
- 9 Body composition: changes in adipose tissue and skeletal muscle volume by whole body MRI.

#### 3.3 SAFETY ASSESSMENT

- 1 Vitals: blood pressure, pulse rate, oral temperature, respiratory rate.
- 2 The physical examination will consist of an evaluation of the head, neck, eyes, ears, nose, throat, chest, heart, lungs, abdomen, skin, extremities, and the neurological and musculoskeletal systems.
- 3 Body weight.
- 4 Laboratory assessment

CONFIDENTIAL
PAGE 27 OF 80

- Hematology: hematocrit, hemoglobin, mean corpuscular hemoglobin concentration (MCHC), mean corpuscular volume (MCV), platelet count, mean platelet volume (MPV), red blood cell (RBC) count, white blood cell (WBC) count, differential WBC count.
- Lipid profile: total cholesterol (TC), triglycerides (TG), high-density lipoprotein (HDL), low-density lipoprotein (LDL), very low-density lipoprotein (VLDL) and non-HDL.
- Liver function tests (LFTs): aspartate aminotransferase (AST), alanine aminotransferase (ALT), alkaline phosphatase (ALP), total bilirubin (with Conjugated bilirubin), gamma-glutamyltransferase (GGT), total protein and albumin.
- Amylase and lipase
- Renal function tests (RFTs): blood urea nitrogen (BUN), serum creatinine, and estimated glomerular filtration rate (eGFR).
- Coagulation panel: activated partial thromboplastin time (APTT), prothrombin time/international normalized ratio (PT/INR), thrombin time (TT).
- Immunosuppression level (tacrolimus, cyclosporine or sirolimus).
- Gut hormones: Ghrelin, glucagon like peptide, leptin, resistin, and adiponectin
- Glycemic control: HbA1c and fasting plasma glucose.
- Urinalysis: urine examination: physical examination (appearance, color, specific gravity and pH); microscopy (epithelial cells, red blood cells, pus or white blood cells, casts and crystals) and chemical examination (protein, glucose, bilirubin, urobilinogen, ketone bodies, nitrite and blood); urine drug test (at screening).
- Creatine phosphokinase (CPK), CK-MB, troponin 1 and NT-proBNP.
- Serum electrolytes: sodium, potassium, calcium, bicarbonate and chloride.
- Serology: human immunodeficiency virus (HIV) type 1 and type 2, HAV IgM, hepatitis B surface antigen (HBsAg), hepatitis C virus (HCV), CMV (IgG), and EBV VCAIgG.
- Pregnancy test: Serum pregnancy test and urine pregnacy test for women of childbearing potential.

Protocol No.: SARO.17.010

CONFIDENTIAL
PAGE 28 OF 80

- 5 Cardiac function: standard 12-lead electrocardiogram (ECG) and 2D echocardiogram (2D ECHO).
- Adverse event(s): Frequency and severity of AEs /serious adverse events (SAEs), dropouts due to AEs/SAEs for all subjects enrolled will be recorded. AE's will be assessed, and reported as appropriate, in accordance with applicable sections of the U.S. Code of Federal Regulations, Title 21 Part 312 for:
  - Causality (relatedness)
  - Severity
  - Seriousness
  - Expectedness

Approved by: [name] [name] Protocol No.: SARO.17.010

CONFIDENTIAL
PAGE 29 OF 80

### 4 STUDY POPULATION

### 4.1 NUMBER OF SUBJECTS PLANNED

A total 15 subjects will be enrolled in this open-label, single-arm study to receive Saroglitazar magnesium 4 mg. Approximately 5 patients will be included in the pharmacokinetic assessment sub-study.

### 4.2 INCLUSION CRITERIA

- 1. Able and willing to give written informed consent and comply with the requirements of the study protocol.
- 2. Male or female, 18 to 75 years of age, both inclusive.
- 3. Patients who are at least 6 months post liver-transplant with evidence of NAFLD in the liver graft.
- 4. Presence of NAFLD determined by Transient Elastography (TE) with a controlled attenuation parameter (CAP) score cut-off at 263 dB/m prior to enrollment.
- 5. Patients with ≤20% variation in the levels of ALT, AST, ALP and total bilirubin between Visit 1 and Visit 1.1, if either Visit 1 or Visit 1.1 laboratory results are elevated above the reference range.
- 6. History of medical compliance with immunosuppression.
- 7. Female subjects of non-child bearing potential or on highly effective contraception. For male subjects with female partners of childbearing potential, willing to follow highly effective contraception measures during the study, either by the male participant or his female partner or both.

### 4.3 EXCLUSION CRITERIA

- 1. Pregnant or lactating females.
- 2. Patient with abnormal transaminases due to secondary intercurrent illness (should be determined over a period within last 12 months prior to screening).
- 3. Patients with clinically significant bile duct strictures as assessed with MRI and elevated liver enzymes during screening.
- 4. Recurrence of non-NASH causes of chronic liver disease after liver transplantation including autoimmune, viral, medications associated with steatosis and steatohepatitis (e.g., amiodarone and doxycycline) and alcoholic liver disease that are clinically active.

Approved by: Protocol No.: SARO.17.010
[name] [name] Version No.: 7.0

CONFIDENTIAL
PAGE 30 OF 80

- 5. Graft cirrhosis as defined by:
  - I.Cirrhosis on historical liver biopsy.
  - II. Evidence of cirrhosis on imaging including portal venous collaterals.
  - III. Prior history of decompensated liver disease including ascites, hepatic encephalopathy or variceal bleeding.
  - IV. Evidence of esophageal varices on prior endoscopy.
- 6. Body mass index (BMI)  $\leq$ 18 kg/m^2.
- 7. Subjects with change in body weight >5% in the 3 months prior to enrollment.
- 8. Subjects requiring corticosteroid or anticoagulation therapy.
- 9. History of myopathies or evidence of active muscle diseases.
- 10. Unstable cardiovascular disease, including:
  - i. Unstable angina (i.e., new or worsening symptoms of coronary heart disease within the past 3 months), acute coronary syndrome within the past 6 months, acute myocardial infarction in the past 3 months or heart failure of New York Heart Association class (III-IV) or worsening congestive heart failure, or coronary artery intervention, within the past 6 months.
  - ii. History of (within prior 3 months) or current unstable cardiac dysrhythmias.
  - iii. Uncontrolled hypertension (systolic blood pressure >160 mmHg and/or diastolic blood pressure >100 mmHg.
  - iv. Stroke or transient ischemic attack within the prior 6 months.
- 11. History of bladder disease and/or hematuria or has current hematuria unless due to a urinary tract infection.
- 12. Active malignancy post-liver transplantation.
- 13. History of malignancy in the past 5 years and/or active neoplasm with the exception of resolved superficial non-melanoma skin cancer.
- 14. History of chronic rejection of liver transplant graft.
- 15. Acute cellular rejection of liver transplant graft within the past 6 months.
- 16. Evidence of Acute cellular rejection (ACR) or chronic rejection (CR) or alternative etiologies to NAFLD must be ruled out within 4-6 weeks prior to enrollment into the study by either a liver biopsy or at the discretion (clinical judgement and according to local standard of care) of the treating hepatologist.
- 17. Any of the following laboratory values:

CONFIDENTIAL
PAGE 31 OF 80

- a. White blood cell count < 2.5 x 10^3/uL
- b. Neutrophil count  $< 1.5 \times 10^3 / \text{uL}$
- c. Serum bilirubin > 1.5 mg/dL
- d. Serum ALT >3X ULN
- e. INR >1.2
- f. Renal impairment as demonstrated by baseline estimated glomerular filtration rate (eGFR) <60 mL/min/1.73m^2
- g. Abnormal screening total creatine kinase
- h. Abnormal screening lipase or amylase
- 18. Poorly controlled diabetes as defined by an HbA1c >8.5% within the past 6 months.
- 19. Subjects with history of excessive alcohol intake, defined by ≥21 units of alcohol per week in males and ≥14 units of alcohol per week in females for two years prior to enrollment, where a "unit" of alcohol is equivalent to a 12 ounce (oz.) beer, 4-oz. glass of wine, or 1-oz. shot of hard liquor.
- 20. Subject tests positive for a urine drug screen.
- 21. Subject has a history of chronic (uncontrolled) pain.

### 4.4 WITHDRAWAL CRITERIA

The Investigator may withdraw a subject from the study for any of the following:

- 1 Subject who reports an SAE and if considered in Investigator or Medical Expert's opinion it is not in the subject's best interest to continue.
- 2 Any subject found to have entered the study in violation of the protocol.
- 3 Termination of the study by the Sponsor or Principal Investigator (PI) or the regulatory authorities or Independent Ethics Committee/Institutional Review Board (IEC/IRB).
- 4 The subject is lost to follow-up.
- 5 Any subject who wishes to withdraw his/her consent for participation in the study.
- 6 In case a subject becomes pregnant, then she will be withdrawn from the study.

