#### 5.5 BLINDING

This is an open-label study, therefore, PI and participants will be made aware what treatment they will be administered.

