#### 7.3 ADHERENCE TO PROTOCOL

The PI and the site staff shall strictly adhere to the protocol and GCP guidelines. All patients will be strictly required to follow the instructions given to them as per this protocol. For any

PAGE 56 OF 80

deviation or violation from the protocol, considered serious, the patient may be withdrawn from the study at the discretion of the Sponsor or the PI.

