### 8.2.1.2 Modified intent-to-treat population (mITT)

The modified intent-to-treat (mITT) population includes:

- 1. All enrolled patients who received at least single dose of the IP.
- 2. Appear for at least one post baseline visit.

All secondary efficacy objectives will be analyzed using mITT population with post-baseline last observation carried forward (LOCF) as an imputation method for missing values.

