### 8.4 DETERMINATION OF SAMPLE SIZE

Due to the exploratory nature of this study, no formal power calculations were used to determine sample size. The number of patients was chosen based on clinical experience with other similar proof of concept studies. Approximately 5 patients will be included in the pharmacokinetic assessment sub-study.

Approved by: [name] [name] Protocol No.: SARO.17.010

CONFIDENTIAL
PAGE 62 OF 80

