### 6.5 Sensitivity Analysis

A sensitivity analysis to explore the robustness of the efficacy results with respect to the protocol deviations will be performed using per-protocol population for the efficacy endpoints.

Statistical Analysis Plan			
Version Number:	1.0	Date:	31 Dec 2021
Protocol Number:	SARO.17.010	Sponsor Name:	Zydus Therapeutics Inc.

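### Withdrawing a dosed patient from the study for an entry violation or serious deviation removes that patient's Week-24-only data from every analysis set, where continued follow-up would keep them

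*Protocol*

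**What the plan says.** Section 4.4 of the protocol opens with "The Investigator may withdraw a subject from the study for any of the following", and item 2 of its list is "Any subject found to have entered the study in violation of the protocol". The synopsis repeats the item. Section 7.3 adds that, for a deviation or violation "considered serious, the patient may be withdrawn from the study at the discretion of the Sponsor or the PI". Ineligibility found before dosing is handled separately as screen failure in 4.4.1, so item 2 of 4.4 reaches patients who have taken drug. Section 7.4 lists the same event, an enrolled patient who did not meet entry criteria, simply as a protocol deviation. No text says which violators are withdrawn and which stay.

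On blinding, section 5.5 states: "This is an open-label study, therefore, PI and participants will be made aware what treatment they will be administered".

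The text on unscheduled visits in section 7.2 says that a patient who discontinues the study early has the Visit 9 procedures. The Visit 9 list in 7.2 covers concomitant medication, examination, vital signs, weight, safety parameters, adverse events, a pregnancy test and glucometer review.

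The mITT set (protocol 8.2.1.2) takes "All enrolled patients who received at least single dose of the IP" with at least one post-baseline visit. The per-protocol set (8.2.1.3) requires that all entry criteria were met. SAP 6.5 states: "A sensitivity analysis to explore the robustness of the efficacy results with respect to the protocol deviations will be performed using per-protocol population".

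**The concern.** Item 2 ends observation, not only treatment, and does so at the discretion of someone who knows the patient's course. Item 1 of the same list (an SAE) at least asks for a judgement about the patient's best interest. Item 2 sets no criterion, time limit or second review. Two patients with the same violation can therefore be handled differently, and the difference could be related to how they are doing.

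Three things are at stake. Week 24 values may be missing for a reason connected with outcome. The one planned sensitivity analysis depends on ineligible patients having data in mITT and being left out of per-protocol; where they have no data, there is nothing to compare. The primary endpoint is safety over 24 weeks, and withdrawal shortens the period in which events are counted.

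**Working it through.** **1. Which endpoints can have a post-baseline value after withdrawal before Week 24?**

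| Endpoint | Post-baseline times | Source | After withdrawal before Week 24 |
|---|---|---|---|
| MRI-PDFF, MRE, whole-body MRI | Week 24 only | Protocol 7.2, Visits 1 and 8 | No value in any set |
| FSIVGTT, metabolic flexibility | Week 24 only | SAP 8.3.5 | No value in any set |
| 2D ECHO (safety) | Week 24 only | Protocol 6.1.4, SAP 8.3.7 | No value in any set |
| Lipids, HbA1c | Weeks 12 and 24 | SAP 8.3.5 | LOCF if withdrawn after Week 12 |
| SF-36 | Weeks 12 and 24 | Protocol 7.2, Visits 5 and 8 | LOCF if withdrawn after Week 12 |
| Liver enzymes | From Week 4 | SAP 8.3.5 | LOCF if withdrawn after Week 4 |

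SAP 6.8 does not allow baseline to be carried forward, so the first three rows cannot be filled by LOCF. The Schedule of Events (protocol Table 1) is not visible in the copy reviewed. The Visit 9 content is taken from the 7.2 visit list and the synopsis text, which name none of the procedures in those rows.

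**2. Effect on the mITT versus per-protocol comparison.** Let V patients of 15 be entry violators whose mean change differs by D from that of eligible patients. If they are followed to Week 24, mITT mean minus per-protocol mean = V × D / 15. The documents give neither V nor D; assume V = 1 to 3 and D = 0.5 to 1 SD.

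- V = 1: 0.5/15 to 1/15 = 0.03 to 0.07 SD
- V = 2: 1/15 to 2/15 = 0.07 to 0.13 SD
- V = 3: 1.5/15 to 3/15 = 0.10 to 0.20 SD

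If they are withdrawn before Week 24, the contrast due to their ineligibility is exactly 0 for the Week-24-only endpoints, because they contribute to neither mean.

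**3. Size of possible selective loss.** The plan has no figure to reproduce: "A total 15 subjects will be enrolled in this open-label, single-arm study", and "no formal power calculations were used to determine sample size". In SD units, the 95% CI half-width for a mean change is t(0.975, n−1)/√n, which is 0.554 at n = 15, 0.577 at 14 and 0.604 at 13.

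- *Worst case.* The patients lost are those with the least favourable of 15 normal changes. The expected largest value is 1.736 SD, so losing it moves the mean of the rest by 1.736/14 = 0.12 SD. The expected sum of the two largest is 2.984 SD, so losing both moves it by 2.984/13 = 0.23 SD. These are 22% and 41% of 0.554. Simulated CI coverage (400,000 runs) falls to 91% and 82%.
- *Milder case (assumed).* Of 1 or 2 randomly chosen violators, only those with a change worse than average are withdrawn. The simulated shift is 0.03 or 0.06 SD, with coverage of about 95%.
- *Selection through a visible marker (assumed).* If withdrawal follows a marker correlated ρ = 0.3 to 0.5 with the lost endpoint, the worst-case shift is multiplied by ρ. That gives 0.04 to 0.06 SD for one patient and 0.07 to 0.11 SD for two.

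**4. Safety.** SAP 8.3.2 counts treatment-emergent events until the patient exits the study, and summaries are crude counts and percentages. A withdrawn patient stays in the safety denominator with a shortened observation window.

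**The case against.** The plan does anticipate discontinued patients. Protocol 8.2.6 keeps anyone who discontinues for any reason in mITT by LOCF if post-baseline efficacy data exist, and drops them from per-protocol. Section 4.5 keeps data already collected. This stands for liver enzymes, lipids, HbA1c and SF-36 once an earlier value exists, although the contrast then mixes ineligibility with shorter treatment. It does not help where no earlier value exists.

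A reader might infer that the mITT versus per-protocol check as a whole loses its meaning. The documents do not support that. Besides the endpoints kept by LOCF, per-protocol also removes patients who stayed in the study with other major violations, and for them the check works on every endpoint.

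A reader might also take 0.23 SD as the likely bias. It is not. Imaging, FSIVGTT and calorimetry have not been repeated when an earlier withdrawal is decided, so nobody can pick out the worst change. The visible signals, such as rising liver tests, are the ones LOCF retains. Rejection or another liver disease that arises after enrolment is not an entry violation either. The text permits selective withdrawal; it does not plan it.

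On safety, the primary analysis uses all dosed patients, existing events are followed to resolution (9.4.3), and SAEs are reported to 4 weeks after treatment ends (9.4.2). That softens the loss. It does not supply new non-serious events after exit, or a post-baseline ECHO.

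Finally, much of the data loss comes from the Visit 9 rule in 7.2, which applies to every reason for discontinuation. That is right, and 7.2 has to be part of the correction.

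**Conclusion.** The concern holds in a limited form. A dosed patient can be withdrawn from the study at discretion, in an open-label trial, for an entry violation or a deviation considered serious. If that happens before Week 24, MRI-PDFF, MRE, whole-body MRI, FSIVGTT, metabolic flexibility and 2D ECHO have no post-baseline value in any analysis set. For the efficacy endpoints among these, including hepatic fat, the SAP 6.5 analysis cannot show the effect of that violation. The window for treatment-emergent events is also shortened.

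The shift of 0.12 or 0.23 SD for 1 or 2 patients is a bound under perfect selection; milder assumed selection gives about 0.03 to 0.06 SD. Both rest on normally distributed changes and on an assumed number of patients, which the documents do not give. Efficacy is exploratory with no hypothesis tests, there is one arm, and SAP sections 3.1 and 5 already list exclusions and discontinuations with reasons. This is a cheap improvement, not a flaw that undermines the trial.

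**What to change.** In section 4.4, its synopsis copy and the last sentence of 7.3, state that after the first dose an entry violation or protocol deviation alone does not end data collection. The patient is asked to continue the scheduled assessments through Visits 8 and 9, provided the patient consents and the investigator judges the procedures safe. The patient stays in the safety set and, once its post-baseline-visit condition is met, in mITT, and is excluded only from per-protocol.

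Reconcile this wording with the early-discontinuation rule in 7.2, which now leads only to Visit 9 procedures, and with 7.4, which lists the same event as a deviation. Classify violations before database lock without regard to outcome. Whether study drug continues is a separate medical decision and is not addressed here.

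The cost is a wording amendment and visits that are already planned, for what is likely to be a few patients.
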